10.2 STATISTICAL HYPOTHESES

Primary Endpoints

Efficacy: Best Complete response (CR) rates at anytime during treatment with single agent or combination therapy as defined by the Lugano response Criteria for NHL (Cheson 2014)

Efficacy will be measured by the proportion of patients who achieve a complete response to ublituximab alone or ublituximab plus umbralisib combination. Under current treatment protocols, if less than 30% of patients experience a complete response, then the treatment is considered a failure. Thus, for the experimental treatment, we define failure as an observed complete response rate less than 30%, and we define the null hypothesis as follows: $H_0: p_0 \leq 0.30$. Under the assumption that treatment with single agent or combination therapy will result in an observed complete response rate of at least 50%, we define the following alternative hypothesis: $H_1: p_1 \geq 0.50$. Complete response rate and associated 95% confidence intervals will be computed for the study.

Secondary Endpoints

Efficacy:

Overall response rates (ORR) (ie CR+ PR) in the entire cohort as defined by the Lugano response Criteria for NHL (Cheson 2014)

Rate of overall response in the entire cohort will be calculated, and a 95% confidence interval for ORR in the cohort will be calculated.

Toxicity:

Ublituximab tolerability as per CTCAE V5.0 criteria

Umbrasilib tolerability as per CTCAE V5.0 criteria

Regimen toxicities, as defined by CTCAE V5.0 will be summarized using tables and descriptive statistics. For each drug, the proportion of individuals experiencing toxicity events will be calculated, and 95% confidence intervals for these toxicity proportions will also be calculated. No formal hypothesis tests will be conducted with toxicity rates

10.3 ANALYSIS DATASETS

The primary efficacy analyses will be performed on the Intent-to-treat (ITT) population, which will include all subjects who have been enrolled for the study.

10.4 DESCRIPTION OF STATISTICAL METHODS

10.4.1 GENERAL APPROACH

The proportion of patients achieving a complete response (and associated 95% confidence intervals for this proportion) will be calculated for the patients being treated in this study. Three different complete response rates and associated 95% confidence intervals will be computed:

- 1—complete response rate to ublituximab alone
- 2—complete response to combination therapy
- 3—complete response to any therapy administered (i.e. complete response rate guided by the algorithmic approach set forth in this protocol)

The proportion of patients experiencing a drug-related SAE or grade 4-5 non-hematologic toxicity will be calculated for the patients being treated in this study along with 95% confidence intervals around this proportion.

10.4.2 ANALYSIS OF THE PRIMARY EFFICACY ENDPOINT

The proportion of patients achieving a complete response will be calculated for the patients being treated in this study. This proportion will be formally compared to a null proportion of 30%. The population proportion and associated 95% confidence intervals will be calculated at study completion.

10.4.3 ANALYSIS OF THE SECONDARY ENDPOINTS

Secondary endpoints will be descriptive in nature, and no formal statistical analyses will be conducted on them.

The proportion of patients achieving an overall response and an accompanying 95% confidence interval will be calculated for the patients being treated in this study.

The proportion of patients experiencing a drug-related SAE or grade 4-5 non-hematologic toxicity will be calculated for the patients being treated in this study, and 95% confidence intervals around this proportion will also be reported.

10.4.4 SAFETY ANALYSES

Regimen toxicities, as defined by CTCAE V5.0 will be summarized using tables and descriptive statistics.

10.4.5 ADHERENCE AND RETENTION ANALYSES

The PI will provide a DSM report to the UCCC DSMC on a six-month basis. The DSM report will include summaries of minutes taken at meetings (if applicable), the participants' demographic characteristics, expected versus actual recruitment rates, treatment retention rates, any quality assurance or regulatory issues (including a summary of any protocol deviations).

10.4.6 BASELINE DESCRIPTIVE STATISTICS

Demographic data will be compiled for participants in the study at baseline, including age, gender, ethnicity, disease status, and comorbid conditions.

10.4.7 PLANNED INTERIM ANALYSES

No interim analyses are planned for this study.

10.4.8 SAFETY REVIEW

10.4.8.1 TOXICITY REVIEW

Response and toxicity data from the 24 treated patients will be assessed and the number of responses achieved will be tabulated.

10.4.8.2 EFFICACY REVIEW

After all 24 patients have been treated, efficacy will be assessed by complete response rate—regardless of treatment with ublituximab alone or in combination. Complete response rate to the treatment algorithm (as well as 95% confidence intervals around this complete response) will be calculated. In addition, complete response to ublituximab alone will be calculated (along with 95% confidence intervals), and complete response and 95% confidence intervals will also be computed for combination therapy alone.

10.4.9 ADDITIONAL SUB-GROUP ANALYSES

Though sample size is small, we plan to investigate complete response rates (and associated 95% confidence intervals) in the FL and MZL cohorts. Confidence intervals will likely be wide given that these cohorts will be subgroups of the original 24 patients.

10.4.10 EXPLORATORY ANALYSES

Secondary endpoints may lead to exploratory analyses outlined in 10.4.3.

Overall response rate, CR rate, PR rate, PD rate, and SD rate will be summarized for both the FL and MZL cohorts upon study completion.

Progression free survival (PFS) is defined as time from enrollment to PD or death of any cause. Patients who pass away without PD will be counted as if PD occurred on date of death. Patients without PD and did not pass away but are lost to follow up will have their information censored at date of most recent tumor assessment.

Overall survival is defined as time from enrollment to death due to any cause.

Median measures for 2-yr PFS and OS as well as remission duration will be assessed by conducting survival analysis. Kaplan-Meier survival methods will be used to estimate the survival function of these time-to-event outcomes.

Baseline disease and patient factors will be summarized.

Rates of transformation to aggressive lymphoma will be calculated.

Any assessment of minimum residual disease or assessment of next-generation sequencing will be analyzed.

QOL analysis will be performed: The change in Quality of life (QoL) scores as measured by FACT-Lym at the start of therapy and at the end of study will be assessed using a paired t-test and a null hypothesis of no change in QoL over the course of the study. Assessment of EuroQOL questionnaire has been shown in the **Appendix** section.

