In newly diagnosed FL, there are multiple clinical factors prognostic of outcome including age, LDH (Lactate Dehydrogenase), β 2-microglobulin, disease bulk, and stage of disease which have been used to develop prognostic tools such as the FLIPI (Follicular Lymphoma International Prognostic Index), FLIPI2, and guidelines to assist in making treatment decisions such as the GELF (Groupe d'Etude des Lymphomes Folliculaires) criteria.⁷ In addition, newer markers such as response by positron emission tomography/computerized tomography (PET-CT), minimal residual disease (MRD) and biomarkers like m7-FLIPI have been recognized to correlate with disease outcome.^{8,9,10}

The present day approach outlined in the NCCN (National comprehensive cancer network) guidelines is based on stage and burden of FL. Recommendations listed in the NCCN guidelines for early-stage FL (Stage I-II) range from watchful waiting, radiation therapy to single-agent rituximab. Based on Lymphocare database, comparable outcomes have been found with either of

these approaches.¹¹ However, none of these strategies have been compared head-to head in a prospective setting.

The NCCN guidelines for patients with advanced-stage disease are based on disease burden (i.e. low tumor burden versus high tumor burden). Patients with low tumor burden FL are most often observed with a watch-and-wait approach¹² or treated with single-agent rituximab.¹³ Patients with high tumor burden FL are most often treated with combination chemoimmunotherapy (R-chemotherapy), lenalidomide plus rituximab, single agent rituximab with the possibility of rituximab maintenance.¹⁴⁻¹⁶

FL is considered an incurable disease in the majority of patients with currently available therapeutic options. For several years it appeared that the overall survival of low grade FL was around 10 years or under¹⁷ and that it might not be significantly affected by therapy. However, more recent studies in the era of antiCD20 monoclonal antibodies have suggested a significant improvement in overall survival now almost approaching 20 years.^{18,19} Overall survival of patients with FL grade 1 or 2 treated by physicians in the Nebraska lymphoma group between 1982 and 2014 suggested that patients treated before the advent of monoclonal antibodies experienced a decreased overall survival compared to patients treated after.²⁰

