3 OBJECTIVES

Primary objectives:

To determine Best Complete response (CR) rates as measured by PET/CT scan at anytime during treatment with single agent or combination therapy

Secondary objectives:

- To determine overall response rates (ORR) in the entire cohort
- To assess safety and tolerability profile of single agent and combination therapy

[figure not shown]
Exploratory objectives:

- To determine ORR and CR rates after induction therapy in FL and MZL cohorts
- To determine ORR and CR rates after combination therapy in the entire FL and MZL cohorts
- To determine Partial response (PR), Stable disease (SD), progressive disease (PD) rate of single agent and combination therapy
- To assess duration of remission of single agent and combination therapy
- To assess 2-yr progression free survival (PFS) and overall survival (OS) of single agent and combination therapy
- To explore baseline disease and patient factors that may predict response to ublituximab alone and with umbralisib
- To assess rates of transformation to aggressive lymphoma
- To evaluate the health-related quality of life (QoL) of subjects as assessed by the following subject-reported questionnaire:
 - FACT-Lym, a standardized instrument for use as a measure of health-related QoL as highlighted in the **APPENDIX** section
- Correlative analysis: M7FLIPI testing at diagnosis may be performed which can help predict CR rates with single versus combination therapy. Patient samples will be tested in a CAP/CLIA-accredited laboratory on a custom next generation sequencing (NGS) panel. This panel consists of 310 genes, which are recurrently mutated across clonal hematopoietic proliferations including clonal hematopoiesis of indeterminate potential (CHIP), acute and chronic myeloid neoplasms, B- and T-cell lymphomas, and plasma cell neoplasms. Specifically included in this panel are the full coding sequences of the seven genes in the m7-FLIPI clinicopathologic riskmodel: *ARID1A*, *CARD11*, *CREBBP*, *EP300*, *EZH2*, *FOXO1*, and *MEF2B*. (Pastore et al. Lancet Oncol 2015).¹⁰ Mutation data will be analyzed by a board-certified molecular pathologist and these results will be incorporated with clinical data to determine the m7-FLIPI score.
- Minimal residual disease assessment may be performed on patient samples.

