7.1.1 RESPONSE ASSESSMENT

The timing of PET/CT and Bone marrow biopsy on each single agent and combination therapy arms of the trial have been outlined in 7.1.

Patients with a global deterioration of health status requiring permanent discontinuation of study treatment (taken off study) without objective evidence of disease progression and without evidence of other causes to attribute to deteriorating health will be counted as progressive disease. Every effort should be made to document the objective progression even after discontinuation of treatment. Deaths of unknown cause and those related to malignancy or treatment-related toxicity will be counted as treatment failure.

Patients will be analyzed with respect to imaging-based CR, overall survival (OS) and progression-free survival (PFS). Overall survival is defined as time from the first chemotherapy administered on trial until death from any cause. For subjects who are still alive at the time of the study analysis or who are lost to follow-up, survival will be censored at the last recorded date that the subject was known to be alive. Progression-free survival is defined as time from therapy until relapse, progression, or death from any cause. Response will be determined by the principal investigator or the co-principal investigators.

Definitions for clinical response for patients with lymphoma are from the Lugano response criteria (Cheson et al. 2014).³⁴ Response assessment will be performed by treating provider, and will be performed at the University of Colorado.

Definitions of Tumor Response and Progression

Responses will be categorized as complete response (CR), partial response (PR), stable disease (SD), or progressive disease (PD). In addition, a response category of nonevaluable (NE) is provided for situations in which there is inadequate information to otherwise categorize response status.

The screening measurement will be taken as a reference for determinations of response. The nadir measurement will be taken as a reference for PD; this measurement constitutes the smallest measurement recorded, including the screening measurement if this is the smallest measurement. For FDG-avid tumors, metabolic criteria for response by PET-CT will take precedence over anatomic criteria for response by contrast CT when assessing CR.

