- Screening bone marrow biopsy must be performed ≤ 6 months prior to study registration.
- 12-lead single electrocardiogram (ECG) will be recorded.
- Research blood samples (may be collected at screening and at all time-points when a PET CT is performed (i.e EOInduction, Prior to C4,8,12 of combination therapy, EOT, 6,12,18 and 24 months and at recurrence/progression) for correlative analysis as described in this protocol. Research samples will be collected and stored under the LTB protocol. Patients must be tissue bank consented prior to sample collection and samples will be collected by the tissue banking team.
- If screening assessment are performed within 48 hours of C1D1, safety laboratory and physical examinations need not be repeated at Cycle 1.
- Measurements can be done off the CT images of a PET/CT. (If Baseline PET/CT for marginal zone lymphoma patients does not demonstrate uniformly FDG avid lesions subsequent assessments on the study will be done with CT scans of the neck, chest, abdomen and pelvic scan with contrast ONLY

Protocol # 18-2128

PI: [name]

Version Date: May 17, 2021

11. Repeat bone marrow only required for MZL patients to confirm CR if initial bone marrow was positive. This will be arranged +/- 7 days of this visit. On the combination arm, a bone marrow biopsy (if initially involved for MZL) will be done 3 months post completion of 12 cycles of therapy.
12. During the induction treatment, patients will dose according to Dosing Schedule.
13. Hematology blood draws can be done before administration (not more than 2 days apart)
14. EOI PET CT will be performed within 8 weeks (+/- 7 days) post completion of single agent induction therapy. If PET positive after the completion of single agent induction therapy, a biopsy of PET positive area may be done at MD discretion. (If Baseline PET/CT for marginal zone lymphoma patients does not demonstrate uniformly FDG avid lesions subsequent assessments on the study will be done with CT scans of the neck, chest, abdomen and pelvic scan with contrast ONLY)
15. The first cycle of Combination therapy will start (+ 2 week) after End of Induction imaging scan for patients not in CR. Patients on combination therapy will be seen at D1, D8 and D15 for C1, and D1 and D15 for C2 and then seen every 4 weeks for the remaining duration of therapy .

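### 2-year PFS and OS per therapy have no defined groups, conflicting time origins and medians as the summary, so a clock started at enrollment credits patients with time before their group existed

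*Combined protocol and SAP*

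**What the plan says.** The synopsis and Section 3 list as an exploratory objective: "To assess 2-yr progression free survival (PFS) and overall survival (OS) of single agent and combination therapy".

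Section 10.4.10 holds the analysis text. For PFS: "Progression free survival (PFS) is defined as time from enrollment to PD or death of any cause". For OS: "Overall survival is defined as time from enrollment to death due to any cause". For the summary: "Median measures for 2-yr PFS and OS as well as remission duration will be assessed by conducting survival analysis". It names Kaplan-Meier estimation. It does not say who belongs to the single-agent or the combination group, and it gives no landmark and no second clock for the combination.

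Section 7.1.1 starts the clocks elsewhere. For PFS: "Progression-free survival is defined as time from therapy until relapse, progression, or death from any cause". For OS: "Overall survival is defined as time from the first chemotherapy administered on trial until death from any cause". Which therapy is meant is not stated, and Section 1.2 presents the regimen as chemotherapy-free.

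Treatment follows response. Section 6.1.1 puts the PET-CT 8 weeks after the day-22 dose and gives the combination to every patient not in CR. Footnote 15 of the schedule of events (Section 7.4) adds: "The first cycle of Combination therapy will start (+ 2 week) after End of Induction imaging scan for patients not in CR".

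**The concern.** A patient can be identified as a single-agent CR or as a combination patient only at the end-of-induction scan or later. Counting such a group's PFS or OS from enrollment includes a stretch in which its members could not have died (or, for the CR group, progressed), because they would then not be in the group. For the combination, that stretch also precedes any umbralisib.

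The alternative, reading single-agent PFS as that of everyone who received induction, does not isolate the single agent either, because patients not in CR move to the combination from about week 11.

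At stake is the published reading. Two curves side by side could look like a treatment contrast when the allocation rule produced much of it. Separately, the planned medians do not answer a 2-year objective.

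**Working it through.** The plan states no figure for PFS or OS, so there is none to reproduce. Its one planning figure, 73% power for the CR test, reproduces (exact binomial, reject at 11 or more of 24: power 0.729, attained alpha 0.074) and is not touched by this point.

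**1. Lead time.** Day 22 is 21 days after day 1. The scan is at 21 + 56 = 77 days, week 11, or 77/30.4375 = 2.53 months. The combination starts up to 14 days later: 91/30.4375 = 2.99 months. The scan window of ±7 days widens this to 2.30 to 3.22 months. Any gap between enrollment and day 1 adds to it.

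**2. OS.** Assume exponential survival with the FL figure in Section 1.1.1, where recent studies "have suggested a significant improvement in overall survival now almost approaching 20 years".
- Deaths in 2 years: 1 − 0.5^(2/20) = 0.067, and 24 × 0.067 = 1.6. P(12 or more of 24) is about 1e-8 at 2 years and 1e-4 at 5 years.
- With the older FL figure of about 10 years (same section): about 1e-5 at 2 years and 0.026 at 5 years.
- Size of the lead-time effect on 2-year OS of combination patients: 0.5^(24/240) = 0.933 from combination start, against 0.5^(21.47/240) = 0.940 to 0.5^(21.01/240) = 0.941 from enrollment, so 0.7 to 0.8 points. With a 10-year median: 0.871 against 0.883 to 0.886, so 1.3 to 1.5 points.

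**3. Combination PFS.** The documents give no first-line PFS, so a median m of 12 to 60 months from combination start is assumed, with S(t) = 0.5^(t/m). With lead g and nobody in progression at entry, the enrollment clock reports S(24 − g) instead of S(24). If a share f enters with progression already counted as the event, it reports (1 − f) × S(24 − g). The two effects cancel at f = 1 − S(24)/S(24 − g).

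| m (months) | S(24) | From enrollment, g = 2.53 to 2.99 | Gain (points) | Break-even f |
|---|---|---|---|---|
| 12 | 0.250 | 0.289 to 0.297 | 3.9 to 4.7 | 0.136 to 0.159 |
| 24 | 0.500 | 0.538 to 0.545 | 3.8 to 4.5 | 0.070 to 0.083 |
| 36 | 0.630 | 0.661 to 0.667 | 3.1 to 3.7 | 0.048 to 0.056 |
| 48 | 0.707 | 0.733 to 0.738 | 2.6 to 3.1 | 0.036 to 0.042 |
| 60 | 0.758 | 0.780 to 0.784 | 2.2 to 2.7 | 0.029 to 0.034 |

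To size the group, take the 36% CR rate that Section 1.1.1 gives for rituximab in FL: 24 × 0.36 is about 9 in CR, leaving 15. Break-even is then 0.029 × 15 = 0.4 to 0.159 × 15 = 2.4 patients. With f = 0.10 and m of 24 months or more, the bias is −1 to −6 points.

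**4. CR-only single-agent PFS.** Assume 30% in CR, event-free to 2.53 months and exponential after that, with non-CR patients exponential from the start.
- Medians 48 (CR) and 24 (non-CR): the CR group from enrollment gives 0.5^(21.47/48) = 0.733. All patients given 0.3 × 0.733 + 0.7 × 0.500 = 0.57. The CR group from the scan gives 0.5^(24/48) = 0.707.
- Medians 36 and 36: 0.66, 0.64 and 0.63.
- Medians 60 and 18: 0.78, 0.51 and 0.76.

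Guaranteed time accounts for 2 to 3 points (first figure less third). The rest of the gap to all patients is selection.

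**5. PFS median.** P(12 or more of 24 events by 24 months) is 0.998, 0.58, 0.14 and 0.03 for true medians of 12, 24, 36 and 48 months.

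**6. Follow-up left.** Section 4.1 follows outcomes for 2 years from enrollment. From combination start that leaves 24 − 2.99 = 21.0 to 24 − 2.53 = 21.5 months.

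**The case against.** The strongest reply is that Section 10.4.10 defines PFS and OS once and never splits them by therapy; the split appears only in the objectives. If the objective means the response-driven sequence as a whole, an enrollment clock is sound. This stands in part: the documents do not say that the groups are formed by the week-11 response. That is the natural reading of objective and design together, and the missing definition is itself the gap.

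A reader might infer that every per-therapy estimate is biased upward. The documents do not support that for combination PFS. Section 6.1.1 sends all patients not in CR to the combination without excepting progression, while Section 5.4.1 lists progression as a reason to stop study treatment. If patients in progression enter, their event precedes the combination and pulls the estimate down. Nor is a single-agent group necessarily all CR: patients who withdraw or stop for toxicity before the combination have also had only the single agent.

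A reader might also infer that the PFS median is out of reach. Section 1.1.1 gives a survival time for FL only, with no PFS and no survival time for MZL, and step 5 shows that the answer depends on the unknown true PFS. The planned Kaplan-Meier curves do allow a 2-year rate to be read off, although the plan does not commit to reporting it.

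Finally, these analyses are exploratory, no test between the therapies is planned, and the shifts are small against the precision. For 15 patients at 60% without censoring, the 95% half-width is 1.96 × √(0.6 × 0.4/15) = 0.25. All of this stands and limits the weight of the point.

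**Conclusion.** The point holds in a limited form. The per-therapy groups are undefined, Sections 7.1.1 and 10.4.10 disagree on the origin of both endpoints, and medians are requested for a 2-year objective.

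If the groups follow the end-of-induction response:
- OS from enrollment is biased upward in both groups. For the combination the direction is certain but the size is about 1 point or less with a 20-year median.
- PFS of a CR-only group is biased upward by 2 to 3 points of guaranteed time, plus selection that may be much larger.
- Combination PFS at 2 years is raised by about 2 to 5 points if nobody enters in progression. Depending on the true PFS, between one and three such patients in 15 would turn the bias downward.

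The OS median cannot realistically be reached in the planned 2 years. The PFS median may or may not be. The figures rest on constant hazards, complete follow-up and the stated assumed medians. The whole-sequence estimate from enrollment is sound, and the primary CR analysis is unaffected. The change should be made, but the trial's main conclusion does not depend on it.

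**What to change.** - State one origin, enrollment or induction C1D1, in both Section 7.1.1 and Section 10.4.10 for whole-cohort PFS and OS, and attribute those estimates to the response-driven sequence.
- Report any subgroup estimate as conditional on end-of-induction response. Start the clock at the end-of-induction scan for patients in CR and at combination C1D1 for combination patients. Do not compare the two.
- Replace the medians with the Kaplan-Meier estimate at 24 months and its 95% CI, giving a median only if it is reached.
- Reconcile Sections 5.4.1 and 6.1.1 on progression at the end-of-induction scan, and state how such patients count in combination PFS.
- Reconcile the follow-up length. Section 4.1 stops at 2 years from enrollment, whereas Section 7.1 plans imaging to 24 months after the end-of-treatment scan and clinic visits to year 5. A 24-month estimate from combination start needs the longer schedule.

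The cost is mostly wording, and the dates needed are already collected. The follow-up and progression rules need a decision as well as an edit. Combination 2-year figures may move by a few points, which is small against the precision of a group of about 15.
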